9. INTERVENTIONS

Study sites (clusters) will be randomly allocated to either the incentive intervention or to the control condition (**Table 1**). All sites will receive a core packet of services provided by population-targeted ICCs (either PWID or MSM).

Table 1. Summary of services in control and intervention conditions

Service/Intervention	Control Condition sites (n=8)	Incentive Intervention sites (n=8)
HIV counseling and testing	X	X
Harm reduction services		
Condoms	X	X
Risk reduction counseling	X	X
Syringe service program (SSP)	PWID sites	PWID sites
Opioid agonist treatment (OAT)	PWID sites	PWID sites
STI screening and syndromic treatment	X	X
TB symptom screening and referral	X	X
Hepatitis C virus (HCV) antibody testing and counseling	PWID sites	PWID sites
Services for HIV-positive clients		
Referral for ART and peer outreach	X	X
Motivational interviewing	X	X
Incentives for achieving HIV treatment milestones		X

9.1 Control Condition

This trial incorporates an active control condition. In a prior trial, we evaluated the acceptability, feasibility, and effectiveness of PWID- or MSM-focused ICCs (2). The goal of ICCs was to provide a menu of population-specific services in non-discriminatory settings. We found that ICCs served large numbers of clients (median of 1,500 per ICC over 2 years), were favorably reviewed in anonymous client surveys, and increased community level HIV testing rates (2). Although the integrated population-focused venue is distinct, the services provided by ICCs are consistent with the standard of care in India. At the present time, pre-exposure prophylaxis (PrEP) is not endorsed by the National AIDS Control Organisation (NACO) in India and is not available in ICCs. In the control condition, the following care package will be routinely available

- HIV counseling and testing
- Harm reduction services
 - Condoms
 - Risk reduction counseling
 - SSP (PWID sites only)
 - OAT (PWID sites only)
- STI screening/syndromic treatment
- Tuberculosis (TB) symptom screen and referral
- HCV antibody testing (PWID sites only)
- Services for HIV-positive clients
- Referral for ART and peer outreach/support
- Motivational interviewing for HIV treatment adherence

9.2 Incentive Intervention

The incentive intervention will include all services available at control condition sites plus HIV care incentives. Cohort participants at intervention sites will be eligible to receive treatment incentives (**Table 2**). Additionally, ICCs assigned to the intervention will offer treatment incentives to additional HIV-positive clients (up to a maximum of 300 persons per site).

Table 2. HIV treatment incentive schema

Target	Eligibility	Incentive criteria	Value	Frequency available	Maximum possible over 24 months
Pre-ART retention	ART-naïve	Attend visit at govt. HIV clinic	INR 250 (USD 3.60)	Once every 6 months	INR 1000 (USD 14.30)
ART initiation	ART naive	Initiate ART at govt. HIV clinic	INR 500 (USD 7.10)	Once (non-repeatable)	INR 500 (USD 7.10)
ART persistence	Initiated ART	Timely monthly refills	INR 150 (USD 2.10)	Once every month	INR 3600 (USD 51.40)
Internal motivation	All	MI counseling at ICC	INR 100 (USD 0.70)	Once every 3 months	INR 800 (USD 11.40)

Similar to our approach in a pilot trial in Chennai (3), vouchers will be redeemable for food, clothing, household goods, and specialty items at the ICC or from collaborating stores. Non-cash incentives support a drug- and alcohol-free lifestyle and were acceptable and effective in the pilot trial. Some items that will be stocked at ICCs for voucher redemption are toothpaste, soap,

shampoo, biscuits, tea, coffee, rice (1kg, 5kg), lentils, wheat flour (1kg packs), shirts, sweaters, and backpacks. Each site will decide on the options for incentives based on local experience/needs. Participants may choose to save incentives in an account to redeem for larger gifts (e.g., mobile phone).

Incentives will be given for verified activities, not self-report alone. Governmental HIV clinics record visits, laboratory results, and dispensations of antiretroviral drugs in notebook that patients keep (government ART book). Entries in the government ART book (and if needed verification by records at the clinic) will be used to verify incentivized activities. Incentives for ART refills will be given if the refill is no more than 3-days late, following a typical 30-day prescription.

10. STUDY PROCEDURES/EVALUATIONS

10.1 Clinical Evaluations and Procedures

Clinical evaluations and procedures for study cohorts in cluster randomized trial

Eligible participants who meet inclusion criteria and provide written informed consent will be enrolled in the local cohort. Cohort participants will complete a baseline study visit, most often on the day of screening, and will be asked to complete follow-up visits at 6 months, 12 months, 18 months, and 24 months, for a total of 5 study visits. However, due to delays from the COVID-19 pandemic, not all participants were able to complete the 18- and 24-month visits. Detailed information on the evaluation and procedures of study visits are shown in **Appendix I**. Study visits will include the following evaluations:

- Biometric capture (fingerprint) to confirm identity
- Blood draw, laboratory assessments described below
- Collection of contact and locator information
- Interviewer-administered survey covering the following domains
 - Demographics
 - Quality of life
 - Engagement/experience with HIV care
 - ART adherence
 - Beliefs about ART
 - Alcohol and drug use
 - Injection- and sex-related risk behaviors
 - Depression symptoms
 - Health care utilization
 - Fentanyl and overdose (from 18 months onward)
- Abstraction of information from government ART book

Clinical evaluations and procedures for mixed methods evaluation of treatment incentives

We will query cohort participants at incentive sites about their experiences with and perceptions of treatment incentives in the 24-month visit interview. Additionally, individuals eligible for the qualitative component will be invited to participate in in-depth interviews (IDI). IDIs will use a semi-structured format to address the following domains:

IDIs with ICC clients at intervention sites

- Perceived purpose of the incentive program
- Process of learning about the incentive program
- Experiences with receiving incentives
- Opinions about the value of incentives and how frequently incentives could be earned
- Impact of incentive program on client opinions and beliefs about HIV care

IDIs with ICC staff

- Familiarity with the incentive program
- Perceived purpose of the incentive program
- Challenges with implementing the incentive program
- Good and bad things about the incentive program
- Opinions about how the program affected HIV-positive clients' behaviors

Clinical evaluations and procedures for RDS survey

The RDS survey will be a cross-sectional assessment of PWID or MSM populations in each study city. Beginning with 2-5 “seed participants,” eligible participants who complete a one-time study visit are eligible to recruit up to 2 network members to the study with coupons (described above). Participants will be reimbursed both for completing the study visit and for each eligible participant that they refer to the study (up to 2). RDS participants who present with a valid recruitment coupon will be asked to undergo the following procedures:

- Biometric scan (fingerprints) to assure individual has not already participated in the study
- Rapid HIV counseling and testing, described below
- Interviewer-administered survey covering the following domains
 - Demographics
 - Peer network information
 - Substance use (including alcohol)
 - Drug-related and sexual risk behavior
 - HIV treatment literacy
 - HIV care continuum outcomes (e.g., experience with HIV testing, HIV care and HIV treatment)
 - General utilization of health care including hospitalizations, physician and non-physician outpatient visits, medications, productivity (full-time, part-time work), out of pocket medical costs, and time and wages lost due to medical appointments including travel as well as utilization of harm reduction services (OAT, syringe service program [SSP])
 - Depression
 - Quality of Life
 - Social Support
 - Stigma

10.2 Laboratory Evaluations

Laboratory evaluations for the study cohort in the cluster randomized trial

- HIV RNA will be measured from plasma at all cohort study visits by the central laboratory (YR Gaitonde Centre for AIDS Research and Education [YRG CARE]) in

Chennai, India using RealTime HIV-1 (Abbott Laboratories, Abbott Park, IL, USA). The HIV RNA result at the 24-month visit will be shared with participants

- CD4 cell counts will be measured at baseline by flow cytometry in a local or regional laboratory. The CD4 test result will be shared with participants.
- At the 6-month, 12-month, and 18-month cohort visits we will measure serum glucose, serum creatinine, and a liver function panel, respectively. These assays will be conducted at local or regional laboratories. Results from these tests will be shared with participants as a value-added benefit of participating in the trial.

Laboratory evaluations for mixed methods evaluation of incentives

None

Laboratory evaluations for RDS survey

- Rapid HIV testing - This point-of-care testing will be used to test all RDS participants. The rapid testing protocol includes the use of 3 rapid test kits in an algorithm: Alere Determine HIV-1/2 (Alere Medical, Chiba, Japan), First Response HIV Card test 1-2.0 (Premier Medical Corporation, Daman, India), and Signal Flow Through HIV 1+2/Immunodot Test Kit (Span Diagnostics, Surat, India).
- HIV-1 RNA - HIV RNA will be measured from plasma in HIV-positive survey participants by the central laboratory (YRG CARE) in Chennai, India, using RealTime HIV-1 (Abbott Laboratories, Abbott Park, IL, USA).
- CD4 cell count - CD4 cell counts will be measured in all HIV-positive participants by the central laboratory (YRG CARE) in Chennai, India using Flow Cytometry (EPICs XL-MCL, Beckman Coulter, Inc., USA).
- Recent HIV infection - Recent HIV infection will be assessed using a validated multi-assay algorithm in all HIV-positive survey participants. The algorithm testing includes Limited Antigen (LAG) Avidity EIA (Maxim Biomedical Inc, Rockville, MD, USA) and the JHU-modified Bio-Rad Avidity assay (Bio Rad Laboratories, Hercules, CA, USA). Individuals are characterized as having recent infection if CD4 count >50 cells/mm³, HIV RNA >400 copies/mL, LAG avidity <2.9 OD-n, and JHU-modified Bio-Rad avidity index <85% (5).

11. ASSESSMENT OF SAFETY

11.1 Safety Assessment Overview

This section provides information on the definition of adverse events (AE), serious adverse events (SAE) and the procedures for reporting. Procedures for prompt reporting of AE and SAE will be standardized across the field sites.

11.2 Definitions

11.2.1 Definition of Adverse Events (AE)

An AE is any unfavorable and unintended sign (including an abnormal laboratory finding), symptom, or diagnosis that occurs in a study participant during the conduct of the study

regardless of the attribution (i.e., relationship of event to medical treatment/study product/device or procedure/intervention). This includes any occurrence that is new in onset or aggravated in severity or frequency from the baseline condition.

11.2.2 Definition of Serious Adverse Events (SAE)

An SAE is defined as any untoward medical occurrence that:

- Results in death
- Is life-threatening
- Requires inpatient hospitalization or prolongation of existing hospitalization
- Results in persistent or significant disability/incapacity
- Is a congenital anomaly/birth defect
- Is an important medical event that may not be immediately life-threatening or result in death or hospitalization but may jeopardize the patient or may require intervention to prevent one of the other outcomes listed in the definition above).

11.3 Reporting Requirements for this Study

The research procedures in our study include 1) qualitative work (interviews with key informants), 2) study visits with cohort participants, and 3) a RDS surveys. These research procedures are minimal risk (involve only a blood draw), and do not include a drug or medical device. Furthermore, study sites (or clusters) are the unit of randomization, not individual participants. Participants at intervention sites have access to the intervention (non-cash HIV treatment incentives), but are not required to seek or accept the intervention. Finally, the study population, HIV-positive PWID and MSM have substantially higher risks of morbidity and mortality than person in the general population. Given these considerations, our reporting obligations for the trial focus only on events that are more likely than not to be associated with i) study procedures, or ii) participation in the intervention. Two types of events will be reportable:

1. Unanticipated problems involving risks to participants or others will be reported to the YRG CARE and JHM IRBs within 10 working days (unless the event is death, in which case # 2 applies). Such events are defined as:
 - a. The information is unexpected in terms of nature, severity, or frequency, given:
 - i. The research procedures described in the protocol and informed consent document; and
 - ii. The characteristics of the subject population being studied
 - b. The information indicates that the participants or others are at greater risk of harm (including physical, psychological, economic, or social harm) than was previously known or recognized.
2. Deaths of study participants in close association with study procedures will be reported to the IRB within 3 working days.

12. CLINICAL MANAGEMENT

12.1 Clinical Management of Adverse Events

Research staff will interact with participants at study visits and during the intervention (dispensing non-cash incentives). Research staff will refer participants to a clinic or hospital for medical conditions that arise.

12.2 Criteria for Discontinuation

12.2.1 Criteria for Permanent Intervention Discontinuation for an Individual Participant

Potential reasons for permanent or premature discontinuation of intervention are:

- Request by the participant to stop.
- Request of site coordinator if s/he thinks the intervention is no longer in the best interest of the participant.
- At the discretion of the IRB/Ethics Committee, Office for Human Research Protections (OHRP), other government agencies as part of their duties, or investigator

12.2.2 Criteria for Premature Study Discontinuation for an Individual Participant

Potential reasons for permanent or premature discontinuation of study are:

- Request by the participant to withdraw.
- Request of site coordinator if s/he thinks study participation is no longer in the best interest of the participant.
- At the discretion of the IRB/Ethics Committee, Office for Human Research Protections (OHRP), other government agencies as part of their duties, or investigator

13. STATISTICAL CONSIDERATIONS

13.1 Overview and General Design Issues

The primary objective of this study is to determine whether offering non-cash HIV care incentives increases survival with viral suppression among HIV-positive PWID and MSM. Key secondary endpoints include engagement in HIV treatment and retention to care as mediators of survival with viral suppression, qualitative evaluation of treatment incentives, and costs and cost effectiveness. We will address these objectives with a phase III, two-arm, matched-pair, 16-site cluster randomized trial. We selected a cluster randomized as opposed to an individually randomized trial for two reasons. First, the cluster randomized design minimizes the likelihood of contamination effects that might occur if incentives were being offered to some but not to other participants at the same site. Second, we hypothesize that offering incentives will have favorable off-target effects at the ICCs, such as encouraging more key population members to visit for HIV-testing. This can be meaningfully assessed in a cluster randomized design, but not in an individually randomized design. Participants who are HIV-positive and have limited or no prior ART exposure will be enrolled and followed for 24 months at the 16 study sites. The control condition includes linkage and support services provided by ICCs and standard HIV

treatment provided free-of-charge by government HIV clinics.

To provide context for the results from the cluster randomized trial, we will conduct a mixed methods evaluation of treatment incentives and cost-effectiveness analyses. In addition, near the conclusion of the trial intervention phase, we will conduct a concurrent epidemiologic survey of PWID or MSM at all study sites using RDS. The survey will provide insight into the community-level impact of the intervention and to trends in HIV testing, prevention, and treatment (by comparing with results of 2 prior surveys conducted in the same cities).

Protocol revisions due to COVID-19: Cohort study participant enrollment was completed in October, 2018. Study activities (follow-up visits and incentive intervention) were suspended indefinitely in March 2020. At the time research activities were suspended, all participant visit windows had closed for the 6- and 12-month follow-up visits. However, 65 and 959 participants had not completed the 18- and 24-month visits, respectively, but had not reached or were within the visit window. Because of this, in Protocol Version 2.0 we revised the primary endpoint from 24 months to 12 months. Data that was collected at 18 and 24 months will be considered in secondary and sensitivity analyses.

13.2 Study Endpoints

Primary and secondary study endpoints will be assessed at follow-up cohort visits on the basis of laboratory testing, structured interviews, and external sources of data, including government HIV clinic treatment records and death reports from family and friends. Exploratory endpoints will be assessed on the basis of i) costing data collected during the study, ii) qualitative IDIs, and iii) RDS surveys conducted in the key populations near the conclusion of the intervention phase.

13.2.1 Primary Endpoint

Survival with suppressed viral load, defined as HIV RNA <150 copies/mL in plasma or serum, at 12 months.

13.2.2 Secondary Endpoints

- Survival with suppressed viral load at 6, 18, and 24 months.
- Proportion with at least one suppressed viral load during study follow-up (6, 12, 18, or 24 months).
- Time to ART initiation, recorded from government HIV treatment records, among cohort participants that were ART-naïve at baseline.
- Retention to HIV care during follow-up, defined as having 1 or more visits to a government ART clinic in each 6-month period of study follow-up.
- ART possession ratio (a measure of medication adherence), defined as the time in possession of ART divided by the follow-up time. Follow-up time will commence at enrollment for ART-experienced participants and at ART initiation for ART-naïve participants. Follow-up time will be censored at the end of trial follow-up, death, or loss-to-follow-up. The amount of time in possession of ART will be determined from ART dispensation logs maintained by government HIV clinics.
- Mortality, defined as a report of a participant's death from a family member or a close

friend. Death records are not maintained by local, state, or national governments in India.

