7. STUDY DESIGN

This is a phase III, two-arm, matched-pair, cluster randomized trial. The study will be conducted at 16 sites across India (8 PWID and 8 MSM). Eligible, HIV-positive PWID or MSM will be recruited at each site prior to randomization. In each site pair, one site will be assigned to the control condition and the other site to the incentive intervention.

1. Control condition – Free-of-charge HIV care and ART available at government HIV clinics. ICCs provide HIV counseling, risk reduction services, and peer outreach to support HIV treatment linkage, adherence and retention.
2. Incentive intervention – Control condition services plus ICCs offer HIV treatment incentives (non-cash vouchers for goods) for completing verifiable HIV care activities.

In addition to the quantitative endpoints from the trial, we will also collect mixed methods data to understand how treatment incentives were perceived by different stakeholders. During the latter part of the intervention phase, we will conduct an epidemiologic survey among PWID and MSM at all study sites using RDS. The survey will provide insight into the community-level impact of the intervention and to trends in HIV testing, prevention, and treatment (by comparing with results of 2 prior surveys). Finally, a cost-effectiveness evaluation will be conducted.

The study duration will be approximately 48 months. Ethnography and preparatory work at the sites will take 6 months. Participants will be enrolled over 12 months and then followed for a 24-month intervention phase. Finally, an epidemiologic survey will be conducted at all sites at the conclusion of the intervention phase that will extend another 6 months.

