8. STUDY POPULATION

We will recruit cohorts of HIV-positive participants at each ICC site, with roll-out of the study arm allocation (incentive intervention or control condition) after or near the conclusion of cohort

enrollment. Cohort participants will be followed for 24 months during the intervention phase in order to accomplish primary and secondary objectives. The exploratory objectives require i) collecting of mixed methods data on HIV care incentives from key stakeholders, ii) conducting an RDS survey at each site targeting either PWID or MSM, depending on the site, and iii) conducting cost-effectiveness analyses.

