13.6 Randomization and Masking Procedures

In cluster-randomized trials with a relatively low number of sites (clusters), substantial imbalances between study arms can emerge easily by chance. To reduce the likelihood of large study arm imbalances for key variables, we restricted the pool of potential allocation combinations by removing combinations with large baseline imbalances. With no restrictions, there were a total of 16 potential allocations (i.e., 4^2) within each stratum (PWID/MSM), or 256 overall allocations. First, to reduce large imbalances within the strata, randomization allocations were dropped ($n=8$, 4 in each stratum) due to imbalances in prevalence of viremic persons or viral suppression (i.e., all sites with higher/lower prevalence were allocated to one arm). This resulted in 12 allocations for each stratum. These allocations crossed (PWID x MSM), resulted in 144 potential allocations (i.e., 12^2). Then, an additional overall restriction was placed in which allocations were dropped ($n=36$) due to imbalances in prevalence of viremic persons or viral suppression (i.e., higher/lower prevalence 6:2 pair ratio in different arms). This resulted in a total of 108 potential allocations. We checked across all these potential allocations for sites that either always or never appeared in the same study arm. No sites always or never appeared in the same

arm - with the exception matched sites, which, by definition, never appeared in the same arm.

Of the 108 allocation combinations that remained after site pairing and restriction, one allocation was selected in a ball drawing ceremony on January 3, 2018 that was refereed by two statisticians who were independent of the study. The ceremony was video recorded and is available at <https://youtu.be/UmXBG2CluNA>. Because of the cluster randomized design, masking participants or research staff was not feasible. However, the randomization team withheld the randomization results for each site pair until cohort recruitment was complete or nearly complete at both sites in the pair. The implementation teams in India recruited cohorts at each site without knowing whether the site would be intervention or control.

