13.9.2 Secondary outcomes

Secondary binary outcomes including i) survival with suppressed viral load at other time points (6, 18, and 24 months), ii) proportion with at least one suppressed viral load during follow-up, iii) proportion retained to HIV care (defined as the proportion with at least one visit to the ART center per 6-month follow-up interval), and iv) mortality will be analyzed similarly resulting in pair-wise differences in proportions with a two-stage procedure for confounder adjustment, if appropriate (criteria for confounders outlined in prior section).

For two other secondary outcomes, we will use similar pair-matched cluster approaches with a two-stage procedure for confounder adjustment. First, we will compare risk of initiating ART at intervention vs. control sites (among the subset that is ART-naïve at baseline) using a Cox proportional hazards model. Second, we will compare ART possession ratio (defined as number of days covered by ART dispensations divided by the number of days under observation) by calculating a mean difference between intervention and control conditions.

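### Time to ART initiation has no stated time origin and no rule for ART starts before the pair's roll-out; if time runs from enrolment, any true hazard ratio is pulled toward 1

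*Combined protocol and SAP*

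**What the plan says.** **Endpoint (13.2.2).** "Time to ART initiation, recorded from government HIV treatment records, among cohort participants that were ART-naïve at baseline". No time origin is given.

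**Analysis (13.9.2).** The plan will "compare risk of initiating ART at intervention vs. control sites (among the subset that is ART-naïve at baseline) using a Cox proportional hazards model", within a pair-matched approach that uses the two-stage procedure for confounder adjustment. It mentions no delayed entry and no exclusion of ART starts before roll-out.

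**Timing of the intervention.** Section 8 describes recruitment of the cohorts "with roll-out of the study arm allocation (incentive intervention or control condition) after or near the conclusion of cohort" enrolment. Section 13.6 says that "the randomization team withheld the randomization results for each site pair until cohort recruitment was complete or nearly complete at both sites in the pair". Section 7 plans accrual as follows: "Participants will be enrolled over 12 months and then followed for a 24-month intervention phase". Section 10.1 adds: "Cohort participants will complete a baseline study visit, most often on the day of screening".

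**Clocks for other endpoints.** The ART possession ratio, in the same list as this endpoint, runs from enrolment (ART-experienced participants) or from ART initiation (ART-naïve participants). Section 13.2.3 starts follow-up for the ICC-level testing and diagnosis endpoints on the date the intervention is rolled out in the pair.

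**The concern.** A participant who enrols early in a pair's recruitment spends the time until roll-out at a site that offers no incentives, whichever arm the site is later assigned to. The ART-initiation voucher (Table 2, section 9.2) cannot affect an ART start in that interval. Such a participant was nevertheless ART-naïve at baseline and so belongs to the subset named in 13.2.2 and 13.9.2.

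If the clock starts at enrolment, these starts enter the Cox model as events with a true hazard ratio of 1 and are averaged with the later events. The estimate then understates whatever the incentive does.

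This matters because starting ART is one of the steps the incentives reward directly. It is also the step on which the pilot reported a hazard ratio of 2.33 (section 5.1), and section 13.1 treats engagement in HIV treatment as a mediator of the primary outcome.

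**Working it through.** **Plan's own figure.** There is none to reproduce. The power calculation in 13.4 covers only the primary endpoint.

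**Does a pre-roll-out interval exist?** Yes, for most participants. Baseline is usually the day of screening, and roll-out comes at or near the end of recruitment in both sites of the pair. Study-wide accrual is planned over 12 months, so the gap between baseline and roll-out can reach about 12 months. It is shorter if a pair recruited quickly, and zero for anyone enrolled after a roll-out that came when recruitment was only nearly complete.

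**Inputs for size.**
- From the documents: true hazard ratio after roll-out 2.33 (pilot, section 5.1); 24 months of follow-up.
- Assumed: gap g uniform on (0, D), with D = 4, 8 or 12 months; constant monthly control hazard h.
- Guide for h: over 12 months, 33% of pilot controls visited a government HIV clinic at least once (section 5.1). If starting ART requires such a visit, that is a ceiling on their initiation. It gives h = −ln(1 − 0.33)/12 = 0.033 per month. The pilot covered one city and PWID only, so this is a guide and not a bound for the present trial.

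**Model.** The hazard is h in both arms before g, and h × 2.33 after g in the intervention arm. Censoring is at 24 months from baseline. A two-arm Cox model is fitted from enrolment on all baseline-naïve participants.

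**Share starting before roll-out.** 1 − (1 − e^(−hD))/(hD) gives 6%, 12% and 18% for D = 4, 8 and 12.

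**Loss.** 1 − ln(estimated HR)/ln(2.33), where ln(2.33) = 0.846:

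| D (months) | HR, enrolment clock | Log HR lost |
|---|---|---|
| 4 | 2.16 | 1 − 0.770/0.846 = 9% |
| 8 | 2.00 | 1 − 0.693/0.846 = 18% |
| 12 | 1.85 | 1 − 0.615/0.846 = 27% |

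**Sensitivity to the assumptions.** A separate simulation (150,000 per arm) assumed 20%, 40% or 60% of controls starting by 12 months, windows of 3, 6 or 12 months, and either a flat hazard or one four times higher in the first two months.
- At 40% with a flat hazard, 2.33 is estimated as 2.18, 2.03 and 1.83 for the three windows. With the early peak it is 1.96, 1.82 and 1.64.
- Over all scenarios with a true value of 2.33, the enrolment clock gives 1.51 to 2.22. A roll-out clock among those still naïve gives 2.31 to 2.35.
- With a true value of 1.5, the enrolment clock gives 1.21 to 1.47 and the roll-out clock 1.47 to 1.51.
- With a true value of 1.0, both clocks give about 1.00 (0.99 to 1.01).

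**Rule of thumb.** The log hazard ratio lost is close to the share of all ART starts that precede roll-out. In the flat-hazard 40% case those shares are 8%, 15% and 29%, and the losses are 8%, 16% and 29%.

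**The case against.** **The enrolment clock is inferred.** Sections 13.2.2 and 13.9.2 name a population, not a time origin, and some text points the other way. Section 8 says: "Cohort participants will be followed for 24 months during the intervention phase in order to accomplish primary and secondary objectives". The Table 2 maxima also assume 24 months of incentives (24 × INR 150 = INR 3600 for refills). If the team starts time at roll-out among those still naïve, the dilution disappears. This stands as a limit on the claim. It does not remove the gap: the section 8 sentence is not carried into the endpoint or its analysis, and dropping earlier starters would depart from the subset as written.

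**Stronger readings.** A reader might infer that proportional hazards fails by design, or that more than half of the effect is lost. The documents support neither. Hazards are non-proportional for this reason only if the incentive works. Under constant hazards, a loss of about 58% needs a full 12-month window within the pair together with h = 0.15, which means 1 − e^(−1.8) = 83% of controls starting within 12 months. Nor do the documents show that many starts come early. Section 9.1 shows only that referral is offered, section 5.2 reports limited uptake of HIV care and ART in these groups, and 13.5 says sites were chosen partly for low linkage to care and ART.

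**The planned analysis was not simulated.** The calculations use one individual-level Cox model without pairs or clusters, so they show the direction and rough size of dilution. They do not give the power lost. This stands.

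**Restricting to those naïve at roll-out has its own difficulty.** ART books are abstracted at study visits, so status at roll-out may be learned only afterwards, when intervention participants have a voucher reason to bring their books. Status itself is settled before incentives are offered; its ascertainment may not be. This also stands, and the fix has to deal with it.

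**Conclusion.** The plan leaves open the time origin and the handling of pre-roll-out ART starts for an endpoint that the incentive targets directly. The written subset admits events the voucher could not have caused. On the enrolment clock, which the possession-ratio definition makes the more natural reading, any true hazard ratio is pulled toward 1.

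The size cannot be derived, because the documents give no initiation rates, pair roll-out dates or ART-naïve counts. About 9% to 27% of the log hazard ratio is lost for windows of 4 to 12 months, assuming a constant hazard, about 33% control initiation by 12 months and a true hazard ratio of 2.33. Under constant hazards the loss is larger only with faster initiation; a peak in initiation soon after enrolment would also increase it.

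The consequence is an understated effect on one secondary endpoint. It is not a false-positive risk, and the primary analysis does not use this model. The change is still worth making, because 13.2.3 already applies a roll-out clock elsewhere.

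**What to change.** In 13.2.2 and 13.9.2:

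1. Start time at the later of enrolment and the pair's roll-out date, using the same date for both sites of the pair, as 13.2.3 does.
2. Include, in both arms, baseline-naïve participants whose dated government HIV treatment records show no ART start before that time and who were not known to have died or withdrawn by then.
3. Apply the planned pair-matched two-stage approach.
4. Report the number of pre-roll-out ART starts by arm.
5. Keep the analysis of all baseline-naïve participants from enrolment as a sensitivity analysis.

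**Cost.** The change is a few sentences of text, plus roll-out dates that the ICC-level endpoints already require. Participants who started ART before roll-out leave this one analysis, and the target population becomes those still naïve at roll-out. Because allocation was withheld from the implementation teams during recruitment and neither site offered incentives before roll-out, the restriction keeps the randomised comparison, provided status is ascertained equally. For that reason ART status at roll-out should come from dated clinic records in both arms, even when it is abstracted at a later visit.
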